Appendix E. Ethics

For home visits, no new assessments are being implemented; only the location is changed. Hence, an Institutional Review Board (IRB) approval is not required prior to implementing the alternative options for assessments. The IRB will be notified for informational purposes if any alternate procedures are implemented.

A COVID-19 Consent Addendum has been approved for investigational center use if alternate procedures or assessments need to be instituted prior to the implementation of this protocol amendment.

This Statistical Analysis Plan (SAP) describes the planned analysis and reporting for Teva Branded Pharmaceutical Products R&D, Inc. study TV48125-PN-20028, (A Multicenter, Randomized, Double-Blind, Placebo-Controlled, Proof of Concept Study of the Efficacy and Safety of Fremanezumab for Treatment of Patients with Fibromyalgia), and was written in accordance with SOP GBP_RD_702 (Statistical Analysis Plan).

The reader of this SAP is encouraged to read the study protocol for details on the conduct of this study, the operational aspects of clinical assessments, and the timing for completing the participation of a patient in this study.

The SAP is intended to be in agreement with the protocol, especially with regards to the primary and all secondary endpoints and their respective analyses. However, the SAP may contain more details regarding these particular points of interest, or other types of analyses (e.g. other endpoints). When differences exist in descriptions or explanations provided in the study protocol and this SAP, the SAP prevails; the differences will be explained in the Clinical Study Report (CSR).

1. STUDY OBJECTIVES AND ENDPOINTS

1.1. Primary and Secondary Study Objectives and Endpoints

The primary and secondary study objectives and endpoints are as follows:

Objectives	Endpoints

The primary objective of the study is to estimate the treatment effect of fremanezumab administered subcutaneously in reducing pain in adult patients with Fibromyalgia (FM).
	
The primary efficacy endpoint is the change from baseline to week 12 in the weekly average of the daily average PI-NRS score over the past 24 hours.

A secondary objective is to evaluate the effect of fremanezumab on other efficacy measures, including pain, quality of life, sleep, fatigue, improvement in health, physical functioning, and mood.
	
The secondary efficacy endpoints are as follows:
 
 • change from baseline to week 12 in the individual components of the Fibromyalgia Impact Questionnaire Revised (FIQR): symptom subscore, impact subscore, and functional subscore score • responder rate of the Patient Global Impression of Change (PGIC) rating (percentage of patients much improved or very much improved) at week 12 • the percentage of patients who experience a $\geq 30\%$ reduction in the weekly average of the daily average PI-NRS score at week 12 • the percentage of patients who experience a $\geq 50\%$ reduction in the weekly average of the daily average PI-NRS score at week 12 • change from baseline to week 12 in the weekly average of the daily worst PI-NRS score over the past 24 hours • change from baseline to week 12 in the Patient-Reported Outcomes Measurement Information System (PROMIS) Sleep Disturbance Short Form (SF) 8a score • change from baseline to week 12 in the PROMIS Physical Function SF12a score • change from baseline to week 12 in the PROMIS Fatigue SF8a score

Objectives	Endpoints
	
 • number (%) of patients who did not complete the treatment (Kaplan-Meier Survival Analysis) due to lack of efficacy

A secondary objective of the study is to evaluate the safety and tolerability of fremanezumab administered subcutaneously in adult patients with FM.
	
The safety and tolerability endpoints are as follows:
 
 • occurrence of adverse events • change from randomization to week 12 in the clinical laboratory tests (serum chemistry, hematology, and urinalysis) • change from baseline to week 12 in vital signs (pulse, respiratory rate, systolic and diastolic blood pressure, and oral body temperature measurements at each visit) • clinically significant changes in physical examination, including body weight • abnormal standard 12-lead electrocardiogram (ECG) findings • tolerability at the injection site including but not limited to pain, erythema, induration, and ecchymosis • occurrence of hypersensitivity/anaphylaxis reactions using standardized criteria (Appendix C of the study protocol) • suicidal ideation and behavior as measured by the Columbia-Suicide Severity Rating Scale (C-SSRS) • number (%) of patients who did not complete the treatment (Kaplan-Meier Survival Analysis) due to adverse events

1.2. [REDACTED]
[REDACTED]

		
 • [REDACTED] • [REDACTED]
		
 • [REDACTED] • [REDACTED] • [REDACTED] • [REDACTED] • [REDACTED] • [REDACTED] • [REDACTED]

1.3. Immunogenicity Objective and Endpoint

The immunogenicity objective and endpoint are as follows:

Objectives	Endpoints
To evaluate the immunogenicity of fremanezumab and the impact of anti-drug antibodies (ADAs) on clinical outcomes	
 • incidence and characteristics of ADAs (eg, titers, kinetics, and neutralizing activities)

1.4. Estimand for Primary Efficacy Endpoint

The combination of treatment policy and hypothetical strategy will be used for the primary efficacy endpoint to account for the intercurrent events. The four attributes of the estimand are defined as follows:

- A. Population:** The patients with fibromyalgia met all inclusion criteria and met none of the exclusion criteria.

Statistical Analysis Plan

The modified intent-to-treat (mITT) analysis set defined in Section 3.2 will be the primary analysis set for efficacy. In the data analyses, the treatment will be assigned based on the treatment to which patients were randomized, regardless of which treatment they actually received.

B. Variable: Change from baseline to week 12 in the weekly average of the daily average PI-NRS score over the past 24 hours.

C. Intercurrent events: Treatment discontinuation due to an adverse event, due to lack of efficacy, or due to other reasons.

For those who discontinue the treatment before week 12, no further efficacy data will be collected. The use of rescue medication for fibromyalgia pain will not be considered as an intercurrent event.

D. Population-level summary: The primary efficacy endpoint, the change from baseline to week 12 in the PI-NRS scores, will be analyzed using a Mixed Model Repeated Measures (MMRM) model with change from baseline in the weekly average of the daily average PI-NRS score over the past 24 hours at weeks 1, 2, 3, 4, 5, 6, 7, 8, 9, 10, 11, and 12 as the dependent variable, sex, age group at FM onset, week, treatment, and treatment by week interaction as fixed factors, and baseline average of the daily average PI-NRS score as a covariate. An adjustment for missing data due to adverse event or due to lack of efficacy on the PI-NRS scores will be on average return to baseline values, while due to all other reasons will be imputed assuming missing at random. With missing data imputed, each of the 500 imputed data sets will be analyzed using the MMRM model. The results from the 500 analyses will be combined using Rubin’s formulae. The least square (LS) mean estimates for the mean change from baseline to each time point, as well as the difference of the estimates between the fremanezumab and placebo group, with the corresponding standard error (SE), p-value and associated 95% confidence interval (CI) will be provided.

Sensitivity Analysis: The primary analysis will be repeated; however, the daily average pain scores measured on the days where the patient took rescue medication will be replaced with his or her PI-NRS score at the time of rescue medication use before the weekly average PI-NRS scores are derived. On days where a patient uses rescue medication more than once, the mean PI-NRS score at the time of rescue mediation use for the day will be used as the pain score in place of the average pain intensity score for that day.

2. STUDY DESIGN

2.1. General Design

This is a 21-week, multicenter, randomized, double-blind, placebo-controlled, parallel-group study to evaluate the efficacy and safety of fremanezumab in adult patients with FM. Fremanezumab 225 mg, fremanezumab 675 mg, or placebo will be administered sc for 4 monthly doses. The study will consist of a 17- to 35-day screening period (Visit 1, phone contact, a Baseline Assessment Period Start [BAPS] Visit [Visit 2]), and a 16-week double-blind treatment period (Visits 3, 4, 5, 6, and 7). Patients enrolled in the study will be male or female patients with FM with an average of the daily average PI-NRS score of ≥ 4 and ≤ 9 during the 14-day baseline assessment period. Patients will be required to wash out of all prohibited concomitant medication(s) prior to the BAPS Visit (Visit 2).

[figure not shown]
Therefore, the total duration of patient participation in the study is planned to be 21 weeks, consisting of the screening period of up to 5 weeks (ranging from 17 to 35 days) and the double-blind treatment period of 16 weeks. The end-of-study (EOS) is defined as completion of the last visit of the last patient.

Note, there was the 14-week follow-up period prior to Study TV48125-PN-20028 protocol amendment 04.

The study schematic diagram is presented in [Figure 1](#).

Study procedures and assessments with their timing are summarized in Table 1 of the study protocol.

Figure 1: Overall Study Schematic Diagram

^a The screening period is up to 5 weeks and can range from 17 to 35 days. The duration of the washout period will be 7 to 19 days; suggested washout periods for commonly used analgesics are listed in the study protocol. Note: For Visits 4 and 5 (when at-home dosing is available), home visits are permitted for patients who are not able to go to the investigational center or if the investigational center staff are not able to see patients at the investigational center.

BAPS = Baseline Assessment Period Start; COVID-19 = Coronavirus Disease 2019; e-diary = electronic diary; EOS = end-of-study; EOT = end-of-treatment; PK = pharmacokinetic; sc = subcutaneous; V = visit.

The follow-up period (14 weeks) in the protocol was removed in Study TV48125-PN-20028 protocol amendment 04. The data collected in the follow-up period will be listed.

2.2. Randomization and Blinding

This is a randomized, double-blind, placebo-controlled study. All the investigational medicinal products (IMPs) will be identical and indistinguishable. Patients, investigators, and all clinical study center (CSC) staff will remain blinded to treatment assignment during the study. Eligible patients will be randomly assigned via a qualified Randomization and Trial Supply Management (RTSM) system in a 1:1:1 ratio to fremanezumab at 225 mg sc or fremanezumab 675 mg sc, or placebo sc. Randomization will be stratified by sex (male/female) and age at FM onset (<40 years old and ≥40 years old).

Patients will be randomly assigned to treatment groups by means of a computer-generated randomization list. The generation of the randomization list and management of the RTSM system will be done by a qualified service provider. The specifications for randomization will be under the responsibility and oversight of Teva Global Statistics.

The sponsor's clinical personnel (and delegates) involved in the study will be blinded to the identity of the IMPs until the database is locked for analysis and the IMP assignment is released. However, if a prioritized sample analysis is needed, bioanalytical and clinical pharmacology personnel may be unblinded.

In the event of an emergency, it will be possible to determine to which treatment group and dose a patient has been allocated by accessing the RTSM system. All investigational centers will be provided with details of how to access the system for code breaking at the start of the study. The Medical Monitor or equivalent should be notified, if possible, prior to unblinding or following unblinding. Any unblinding of the IMP performed by the investigator must be recorded in the source documents.

2.3. Data Monitoring Committee

There will be no Independent Data Monitoring Committee for this study.

2.4. Sample Size and Power Considerations

The sample size of 80 subjects per treatment group was selected based on expert consensus agreement at a scientific advisory board meeting; this sample size is expected to provide sufficient precision to estimate the treatment effect of fremanezumab versus placebo. Moreover, assuming a standard deviation (SD) of 2.2 for change from baseline in the weekly average of the daily average PI-NRS score, 80 patients per treatment group will provide at least 90% probability to observe the half length of the 95% confidence interval (CI) of the treatment difference between fremanezumab 225 mg sc or fremanezumab 675 mg sc and placebo less than 0.74. In total, 240 patients will be enrolled in this study in a 1:1:1 randomization ratio.

2.5. Sequence of Planned Analyses

2.5.1. Planned Interim Analyses

There were two interim analyses for futility performed in this study. The details of the interim analyses were specified in separate interim statistical analysis plans. To ensure study integrity, the interim analyses were performed by an independent third party; the study team were kept blinded. The decision was made to end this study for futility following the results of the second interim analysis.

2.5.2. Final Analyses and Reporting

This study has been early terminated due to futility. All analyses identified in this SAP will be performed after study closure. This SAP and any corresponding amendments will be approved before database lock, in accordance to SOP GBP_RD_702 (Statistical Analysis Plan).

The randomization codes will not be unblinded until this SAP has been approved, the database is locked, and the analysis populations are determined.

3. ANALYSIS SETS

3.1. Intent-to-Treat Analysis Set

The intent-to-treat (ITT) analysis set will include all randomized patients.

In the ITT analysis set, treatment will be assigned based on the treatment to which patients were randomized, regardless of which treatment they actually received.

Demographics and baseline characteristics will use the ITT analysis set.

3.2. Modified Intent-to-Treat Analysis Set

The modified intent-to-treat (mITT) analysis set is a subset of the ITT analysis set including only patients who received at least 1 dose of study drug and at least 1 post-baseline entry of daily average pain intensity using the PI-NRS.

In the mITT analysis set, treatment will be assigned based on the treatment to which patients were randomized, regardless of which treatment they actually received.

All efficacy analyses will use the mITT analysis set unless noted otherwise.

3.3. Safety Analysis Set

The safety analysis set will include all randomized patients who received at least 1 dose of study drug. In the safety analysis set, treatment will be assigned based on the treatment patients actually received, regardless of the treatment to which they were randomized.

All safety analyses will use the safety analysis set unless noted otherwise.

3.4. Per-Protocol Analysis Set

The per-protocol (PP) analysis set is a subset of the mITT analysis set including only patients without major protocol violations which will be determined by data review and documented before study unblinding. The PP analysis set will serve as supportive for the efficacy analyses.

In the PP analysis set, treatment will be assigned based on the treatment patients actually received, regardless of the treatment to which they were randomized.

The primary efficacy endpoint and selected secondary efficacy endpoints will be analyzed using PP analysis set.

4. GENERAL ISSUES FOR DATA ANALYSIS

4.1. General

Descriptive statistics for continuous variables include n, mean, SD, standard error (SE), median, minimum, and maximum. In addition, for fremanezumab concentration, percentage coefficient of variation (%CV) and geometric mean will also be calculated. Descriptive statistics for categorical variables include patient counts and percentages, missing category will be displayed as appropriate.

Summaries of potentially clinically significant abnormal values will include all postbaseline values (including scheduled, unscheduled, and early termination visits).

For by-visit analyses, if there are multiple assessments at a scheduled postbaseline visit then the last non-missing scheduled assessment at that visit will be used for the summary. If a visit has scheduled and unscheduled assessments, the scheduled assessment will be used for the analysis. If a visit only has unscheduled assessments, the unscheduled assessments will be used for analyses; if there are more than one unscheduled visits, the assessment from the last unscheduled visit will be used for analyses.

4.2. Specification of Baseline Values

The baseline values are defined as the last non-missing assessments before the first dose of IMP unless otherwise specified.

Baseline value for the average of the daily average PI-NRS pain score is defined as the average of the daily average PI-NRS score over the last 14 days before the first dose of IMP drug (day -14 to day -1) and will be calculated using formula [1].

Baseline value for the average of the daily worst PI-NRS pain score is defined as the average of the daily worst PI-NRS score over the last 14 days before the first dose of IMP (day -14 to day -1) and will be calculated using formula [1].

The baseline values for the following variables are measured on the day of the first study drug (day 1) before the first dose of study drug.

- individual components of the FIQR: symptom subscore, impact subscore, and functional subscore score
- PROMIS Physical Function SF12a score
- PROMIS Fatigue SF8a score
- HADS score
- EQ-5D-5L
- POMS-2A Short Form score

The baseline value for IMD assessment rating is measured at the screening visit.

PROMIS Sleep Disturbance SF 8a score are collected on e-diary weekly during BAPS. The baseline PROMIS Sleep Disturbance SF 8a scores will be the mean of the weekly scores recorded during last 14 days before the first dose of IMP drug (day -14 to day -1).

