^b Patients will be instructed to start the washout period during the screening period phone contact. The duration of the washout period will be 7 to 19 days; suggested washout periods for commonly used analgesics are listed in [Table 4](#). Laboratory values will be checked prior to the phone call by the investigator. Visit 2 will be scheduled and the monitoring plan for washout will be defined by the investigator. The washout period will need to be completed before the BAPS Visit (Visit 2). Training and Instructions will be provided to patients regarding the monitoring of withdrawal symptoms during the washout period.

^c For Visits 4 and 5 (when at-home dosing is available), home visits are permitted for patients who are not able to go to the investigational center or if the investigational center staff are not able to see patients at the investigational center (see [Section 3.5](#)).

^d All assessments listed before IMP administration in the Study Procedures and Assessments are to be performed before IMP administration.

^e For unscheduled visits, procedures and assessments will be completed as needed, at the investigator’s discretion. For further details, see [Appendix B](#).

^f Patients who do not require a washout may be scheduled for the BAPS Visit (Visit 2) following review by the Fibromyalgia Eligibility Review Committee ([Section 5.8.1](#)).

^g Training patients on accurate pain reporting and placebo response reduction on the site’s tablet will occur at Screening (Visit 1), the BAPS Visit (Visit 2), and as needed for subsequent retraining throughout the study.

Clinical Study Protocol with Amendment 05

- ^h Training for the e-diary will occur at Screening (Visit 1), the BAPS Visit (Visit 2), and as needed for subsequent retraining throughout the study. Site personnel will also instruct patients on the requirement for timely and daily completion of the e-diary. During the BAPS Period, a minimum of 12 of 14 days' compliance with e-diary recording is required. At least 75% compliance with e-diary recordings on a weekly basis is expected after the randomization period. Site personnel will monitor patients' compliance that e-diary entry is at least 75% every week during the double-blind treatment period. If weekly 75% compliance is not maintained, a reminder and any other corrective actions, as deemed necessary, will be issued to the patient.

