- ^s A serum pregnancy test may be completed as a confirmatory test, if warranted. In the event pregnancy is confirmed, the IMP will not be administered, and the patient will undergo early termination from the study.
- ^t Postmenopausal women only (at least 1 year since last menses and FSH level above 35 U/L).
- ^u Review of study compliance includes review of e-diary recordings, rescue medication use, concomitant medication use, and use of non-pharmacologic therapies (including normal daily exercise routines, chiropractic care, physical therapy, psychotherapy, and massage therapy).
- ^v The PROMIS Sleep Disturbance SF8a (e-diary) should be performed weekly on awakening. Collection of the PROMIS Sleep Disturbance SF8a will start the day of the BAPS Visit (Visit 2) to assess the previous week's sleep and is completed in the e-diary.
- ^w At the Screening Visit (Visit 1), the IMD (tablet) will be administered by the investigator; any condition that the patient has been diagnosed with will be recorded. At Visit 6 and the EOT/EOS or ET Visit (Visit 7), the IMD will be administered by the investigator; any condition recorded at Visit 1 will be assessed for improvement or non-improvement.
- ^x Blood samples (4 mL) for plasma drug concentration will be collected at designated visits. Blood samples will be collected before dosing when IMP is administered. Samples from patients who were randomized to receive placebo will not be analyzed.
- ^y Blood samples (5 mL) for serum ADA assessment will be collected prior to dosing at the designated visits, as well as upon observation of any severe hypersensitivity reaction or anaphylaxis. Samples from patients who were randomized to receive placebo will not be analyzed.

z

^{aa} Adverse events will be captured from the time informed consent is signed until end-of-study. Postdose inquiries will be made before the patient leaves the investigational center.

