6.1.5. Patient-Reported Outcomes Measurement Information System

6.1.5.1. PROMIS Sleep Disturbance Short Form 8a

The PROMIS Sleep Disturbance SF8 Scale contains 8 items with a score range of 8 to 40 and measures quality of sleep and sleep-related impairment. The PROMIS Sleep Disturbance instrument assesses self-reported perceptions of sleep quality, sleep depth, and restoration associated with sleep. This includes perceived difficulties and concerns with getting to sleep or staying asleep, as well as perceptions of the adequacy of and satisfaction with sleep. Sleep Disturbance does not focus on symptoms of specific sleep disorders, nor does it provide subjective estimates of sleep quantities (total amount of sleep, time to fall asleep, amount of wakefulness during sleep). The Sleep Disturbance SF8 assesses sleep disturbance over the past 7 days ([PROMIS-Sleep Disturbance Scoring Manual](#)). Collection of the PROMIS Sleep Disturbance SF8a will start the day of the BAPS Visit (Visit 2) and will be administered weekly via the e-diary Morning Report to assess the previous week's sleep.

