6.1.2. Baseline and Analysis Weeks for Data Collected Daily

Baseline is defined as the last 14 days before the first dose of IMP (day -14 to day -1). Day 1 will be defined as the day of first dose of IMP (Visit 3).

For data collected daily (eg. PI-NRS scores), analysis weeks will be derived using algorithm in Table 2. Analyses will be based on the derived analysis weeks.

Table 2: Analysis Weeks

4-Week Interval	Visit	Dose (n)	Target Injection or Visit Day	Actual Injection or Visit Day	Analysis Week	Analysis Week Interval
1 ^a	3	1	1	1	1	[1, v-22]
					2	[v-21, v-15]
					3	[v-14, v-8]
					4	[v-7, v-1]
2 ^a	4	2	29	v (2 nd dosing day)	5	[v, x-22]
					6	[x-21, x-15]
					7	[x-14, x-8]
					8	[x-7, x-1]
3 ^a	5	3	57	x (3 rd dosing day)	9	[x, y-22]
					10	[y-21, y-15]
					11	[y-14, y-8]
					12	[y-7, y-1]
4 ^b (last dose)	6	4	85	y (4 th dosing day)	13	[y, y+6]
					14	[y+7, y+13]
					15	[y+14, y+20]
					16	[y+21, y+27]
5	5	EOT	113		-	-

^a In 4-week intervals before the last dose, the 4th week will be 7 days before the date of the injection, and counting backward by 7-day increments to define remaining weeks. The 1st week of these 4-week intervals will include all remaining days in the interval.

^b The weeks after the last dose, an analysis week will be defined as a 7-day interval counting onward.

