The PROMIS sleep disturbance Short Form 8a (SF8a) scale contains 8 items and assesses sleep disturbance over the past 7 days. One item assessing overall sleep quality use a scale of *very poor, poor, fair, good, or very good*. Other 7 items use a scale of *not at all, a little bit, somewhat, quite a bit, or very much*. Each item of the PROMIS sleep disturbance SF8a is on 5-point scales (1 to 5), with 1 for the lowest sleep disturbance and 5 for the highest sleep disturbance. The total score ranges from 8 to 40 (highest sleep disturbance). Collection of the PROMIS sleep disturbance SF8a will start the day of the BAPS Visit (Visit 2) and will be administered weekly via the e-diary. The total raw score ranging from 8 to 40 (highest sleep disturbance) will be calculated as the summation of 8 non-missing scores. If any of 8 items has a missing score, the total raw score will be missing. The calculated total raw score will be converted into t-score

using the scoring table ([PROMIS-Sleep Disturbance Scoring Manual](#)). All questions must be answered in order to produce a valid score using the scoring table. The analysis will be based on t-score.

The change from baseline to week 12 in t-score of the PROMIS sleep disturbance SF8a will be analyzed using MMRM method in manner analogous to the analysis as described in Section 6.3.1. The dependent variable is the change from baseline in the t-score of the PROMIS sleep disturbance SF8a at analysis weeks 1 to 12 (12 levels). BASE is the t-score of the PROMIS sleep disturbance SF8a at baseline. Missing will be considered as missing at random. The results from all visits will be presented using descriptive statistics.

Summary statistics will include data from all analysis weeks.

6.3.6. Change from Baseline to Week 12 in the Patient-Reported Outcomes Measurement Information System Physical Function SF12a Score

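### The PROMIS Sleep baseline is chosen by the day a form is recorded, not by the 7 days it describes: with Visit 2 on day -14 it covers days -21 to -8, and no rule maps the weekly forms to analysis weeks

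*SAP*

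**What the plan says.** - **Baseline.** SAP 4.2: "The baseline PROMIS Sleep Disturbance SF 8a scores will be the mean of the weekly scores recorded during last 14 days before the first dose", given there as day -14 to day -1. The selection is by recording date.
- **The instrument.** Protocol 6.1.5.1: "The Sleep Disturbance SF8 assesses sleep disturbance over the past 7 days". Protocol Table 1, footnote v: "Collection of the PROMIS Sleep Disturbance SF8a will start the day of the BAPS Visit (Visit 2) to assess the previous week", then weekly on waking.
- **Calendar.** Visit 2 is day -14 with a window of 2 days either side, and there is no day 0 (SAP 4.4). Washout has to be finished before Visit 2 (Protocol Table 1, footnote b).
- **Post-baseline weeks.** SAP 6.3.5: "The dependent variable is the change from baseline in the t-score of the PROMIS sleep disturbance SF8a at analysis weeks 1 to 12". The only definition of analysis weeks is Table 2 in SAP 6.1.2, which is introduced for daily data and followed by "Analyses will be based on the derived analysis weeks". SAP 4.4 has the same restriction to daily data. Data after week 12 are summarised but kept out of inference (SAP 4.4 and 6.1).
- **Comparable instruments.** FIQR and PROMIS Fatigue also look back 7 days. Their baseline is taken on day 1 before dosing (SAP 4.2) and their week 12 at Visit 6 (SAP 6.3.1 and 6.3.7).

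**The concern.** A day -14 to -1 window suits the pain diary, where each entry covers about 24 hours. For a form with a 7-day look-back, selecting on the recording date moves the period measured back by up to a week.

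The stake is what the reported change in sleep from baseline to week 12 means. On the nominal calendar the baseline includes a week before the baseline assessment period, which is washout time for patients whose washout runs up to Visit 2. It also leaves out the week closest to dosing. The same question arises after baseline, where the SAP does not say which analysis week a weekly form belongs to.

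**Working it through.** **Inputs.** Forms every 7 days from Visit 2, with no day 0; a form completed in the morning describes the 7 days before it; nominal doses on days 1, 29, 57 and 85. The fixed 7-day spacing is an assumption, since the documents say only that the form is weekly.

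**1. Table 2 at the nominal doses** (v = 29, y = 85):
- week 1 = [1, v-22] = days 1-7
- week 11 = [y-14, y-8] = days 71-77
- week 12 = [y-7, y-1] = days 78-84
- week 13 = [y, y+6] = days 85-91

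The grid reproduces as contiguous 7-day weeks.

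**2. Baseline, nominal Visit 2.** Forms fall on days -14, -7, 1, 8 and so on. SAP 4.2 takes those of day -14 (describing -21 to -15) and day -7 (describing -14 to -8). Together they describe days -21 to -8, of which only 7 lie in days -14 to -1. The form describing days -7 to -1 is completed on day 1 and is not used.

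**3. Baseline across the Visit 2 window.**

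| Visit 2 | Baseline forms | Days described | Of 14, before Visit 2 | Of 14, within -14 to -1 |
|---|---|---|---|---|
| -16 | -9, -2 | -16 to -3 | 0 | 12 |
| -15 | -8, -1 | -15 to -2 | 0 | 13 |
| -14 | -14, -7 | -21 to -8 | 7 | 7 |
| -13 | -13, -6 | -20 to -7 | 7 | 8 |
| -12 | -12, -5 | -19 to -6 | 7 | 9 |

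**4. Analysis weeks, if Table 2 is applied by completion day** (nominal doses, cycle from Visit 2):

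| Visit 2 | Form labelled week 1: day (untreated days of 7) | Form labelled week 12: day, days described (days in week 12) |
|---|---|---|
| -16 | 6 (2) | 83, 76-82 (5) |
| -15 | 7 (1) | 84, 77-83 (6) |
| -14 | 1 (7) | 78, 71-77 (0) |
| -13 | 2 (6) | 79, 72-78 (1) |
| -12 | 3 (5) | 80, 73-79 (2) |

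On the nominal calendar the form that does describe days 78-84 is completed on day 85, falls in week 13 and is excluded from inference. A cycle restarted on day 1 gives days 1, 8, ..., 1 + 7×11 = 78, 1 + 7×12 = 85, so the same week-1 and week-12 labels follow whatever the Visit 2 date.

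**5. Dose timing.** With Visit 2 on day -14, dose 3 on day 57 and dose 4 anywhere in days 78-92, the form labelled week 12 shares between 0 and 6 of its 7 days with week 12, never all 7. With dose 2 on day 22, week 1 is [1, 0] and empty; on day 36 it is days 1-14 and holds two forms.

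**6. Comparison.** On the nominal calendar FIQR and PROMIS Fatigue cover days -7 to -1 at baseline and days 78-84 at week 12. Under the reading in step 4, sleep at week 12 lags them by a week.

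**The case against.** The strongest reply is that the SAP contains no faulty post-baseline rule. Table 2 is expressly for daily data, sleep is weekly, and further e-diary detail is left to a Study Manual. That is right: step 4 is conditional. A reader might infer that the SAP itself makes week 12 report week 11; the documents do not support that as a stated rule. A cycle anchored on day 7, for example, would give forms on days 7, 14, ..., 84 and largely remove the lag. What stands is that the analysis weeks named in SAP 6.3.5 have no other definition, and that two natural anchors give the lag. The baseline result does not depend on Table 2 or on whether the cycle restarts at randomization.

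Second, washout is not universal. Some patients need none (Protocol Table 1, footnote f), washing out everything is not mandatory (Protocol 5.7.3), and several sleep medications may continue (Appendix N). A reader might infer that part of any within-arm sleep improvement is recovery from drug withdrawal. Appendix I does prohibit several hypnotics and benzodiazepines, so it is possible, but the documents give neither the share washing out nor the size or direction of an effect.

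Third, the rule is the same in every randomized arm, baseline is a covariate, and a one-week lag after three monthly doses is small. This stands, and it limits the severity.

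**Conclusion.** The baseline part holds on the text. On the nominal calendar the sleep baseline covers days -21 to -8 instead of days -14 to -1. With Visit 2 on day -13 or -12 it still takes in a full week before Visit 2; on day -15 or -16 the shift is 1 or 2 days. The week-1 and week-12 parts hold only if Table 2 is applied by completion day with a 7-day cycle; failing that, the finding is a missing assignment rule.

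The effect falls mainly on within-arm change, the week-1 contrast (which can contain no treated time), precision, and consistency with FIQR and PROMIS Fatigue. A reader might infer a biased treatment comparison at week 12; none is shown, because the shift is common to all arms. The size in T-score points cannot be computed, since the documents give no sleep SD, washout share or withdrawal effect.

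Severity is minor: one secondary endpoint in a proof-of-concept trial that ended for futility (SAP 2.5).

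**What to change.** In SAP 4.2 and 6.3.5, assign each sleep form to the period that holds most of its 7-day recall.

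- **Baseline:** the mean of forms whose recall lies mainly in days -14 to -1. A day-1 form counts only if its timestamp precedes the first dose; the check is needed because the morning report stays open until 1300h and its make-up runs in the evening (Protocol 3.6.1). On the nominal calendar this gives the forms of day -7 and day 1, covering days -14 to -1.
- **Forms after dosing that recall mainly untreated days** (day 2 or 3 when Visit 2 was on day -13 or -12): state that they count neither as baseline nor as week 1. Baseline then rests on the form of day -6 or -5.
- **Week 12:** the form recalling mainly [y-7, y-1], usually completed at about the dose 4 visit (Visit 6, day 85).
- **Two forms in one week:** use the one with the larger overlap. **No form:** treat the week as missing.

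The cost is a few lines of SAP text and derivation code, with no new data. SAP 2.5.2 places SAP approval before database lock and unblinding, so the change could be made blind.
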